or antibodies. So far, however, patients with immune-system disorders have not been sufficiently represented in the clinical trials for COVID-19 antiviral drugs. At the appendix “Material” of ACCT-1 trial of remdesivir, immune-depressed patients are only a 7% of patients of the 1,062 patients included (32 in the remdesivir arm and 41 in the placebo arm) (35). The number is almost the same for patients with neoplasm malignant with 43 patients included in the remdesivir arm and 37 in the placebo arm representing 8% of the study population (35). Throughout the study analysis, patients with immune-system disorders were grouped with patients with other more frequent comorbidities such as hypertension and obesity and no subgroup analysis was performed (35). A more recent trial, published in 2022 (remdesivir plus dexamethasone *versus* dexamethasone alone also did not have a subgroup of immune-system disorders as comorbidities described (36). So, although the efficacy of remdesivir has been questioned due to conflicting data (35, 37), this RNA polymerase inhibitor and other antivirals such as molnupiravir ([NCT04405739](#)) (38) should also be studied in clinical trials of immunocompromised hosts who may reap the greatest benefit from such interventions. Regarding the use of monoclonal antibodies, which are already available for administration to both immunocompromised and immunocompetent patients in the United States via an emergency use authorization (EUA), they should now be expanded via clinical trials to encompass settings beyond those outlined in the EUA (e.g., early hospitalisation, supplement oxygen requirement in patients with prolonged replication), with a focus on immunocompromised patients who may benefit the most from them. It should be pointed out, however, the marked loss of activity of many monoclonal antibodies (MAbs) against SARS-CoV-2 Omicron variants that underscores the importance of developing MAbs that target conserved regions of spike receptor-binding-domain (39).

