The End of Study (EOS) is Day 60 (± 3) or date of early study termination unless ongoing SAEs, if applicable.

The End of Trial (EOT) will be when the Last Patient Last Visit (LPLV) has occurred.

All patients will receive the best available care as per applicable local, institutional, national, supranational COVID-19 treatment guidelines.

Patients assigned to the experimental arms will receive, in addition to BSC, plitidepsin as a 60-min IV infusion, during Days 1 to 3.

Patients randomised to the control arm may receive a regulatory-approved antiviral treatment in addition to the BSC.

For prevention of infusion-related (i.e., plitidepsin-related) reactions (IRRs), allergic reactions and emesis reactions, administration of premedications is mandatory in the experimental arms.

All consenting patients discontinuing early from the study before the EOS visit should complete the early termination/withdrawal procedures.

Independent Data Monitoring Committee (IDMC)

An IDMC will be established to provide study oversight considering that this is a multicentre, randomised study being performed in a population at high risk for morbidity and mortality. The IDMC will be established and operated in compliance with the FDA Guidance for Industry "Establishment and Operation of Clinical Trial Data Monitoring Committees".

The IDMC will be composed of individuals external not only to the study Sponsor, but also to the trial managers (including Sponsor's and Contract Research Organisation's [CRO] medical monitors), and study investigators, and will be comprised of at least 1 clinician specialised in the treatment of COVID-19 patients, 1 clinician specialised in assessment of clinical study safety issues, and 1 biostatistician specialised in analysis of clinical trials. One IDMC member will serve as chair and will prepare minutes of each IDMC meeting, which will be provided to the study Sponsor, Sponsor's medical monitor, and CRO project manager only at the end of the study.

The IDMC will be held before enrolling the first patient on study to discuss the protocol and analytic plan, ICF, and plans for IDMC monitoring of study safety and effectiveness data.

The IDMC will have responsibility for:

- Review of all SAEs.

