- Change respect to baseline* in inflammatory and immunological (C- reactive protein [CRP], procalcitonin, lactate dehydrogenase [LDH], ferritin, neutrophil-to-

lymphocyte ratio, ALC, D-dimer, and multiplex cytokines assay, by Day 4 (± 1), 8 (± 1), 15 (± 1) and 30 (± 2) and 60 (± 3).

- Change respect to baseline* in individual serological assessments against SARS-CoV-2, by Days 30 (± 2), and 60 (± 3).
- Change respect to baseline* in individual T-cell response against SARS-CoV-2 by Days 30 (± 2), and 60 (± 3).
- Change respect to baseline* to Days 15 (± 1), and 30 (± 2) in chest X-ray findings (Brixia score, centrally assessed) ([Appendix 9 – Brixia Score](#)).
- Percentage of patients requiring modification of the therapy (drugs, dose or schedule) for the underlying disease.
- Time in which pre-scheduled therapies for the control of the underlying disease were not able to be administered.
- Risk for mortality / clinical deterioration according to individual clinical characteristics and laboratory observations present at baseline*, scores of validated scales (e.g., ISARIC-4C), as well as features related to COVID-19 [including SARS-CoV-2 variant (if available), vaccination status, duration of the infection, and inflammation-related parameters [neutrophil-to-lymphocyte ratio (NLR), protein C reactive, interleukine-6 (IL-6) and lymphocytes], the underlying disease, and other co-morbidities.
- Limited-sampling pharmacokinetics assessment (See [Section 7.6](#)).
- PK-PD analysis.

*Baseline = latest test performed between screening and drug administration

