4.1 INCLUSION CRITERIA

To be eligible for inclusion into this study, each patient must fulfil the following inclusion criteria within 48 hours prior to randomisation:

General inclusion criteria:

1. Signed informed consent obtained prior to initiation of any study-specific procedures and study treatment;
2. Patient aged ≥ 18 years;
3. Patient diagnosed COVID-19, with the following characteristics: a) A regulatory approved test, collected no more than 3 days prior to study randomisation, with either a Ct value ≤ 30 or a positive antigen test;
b) Presence of any of the selected signs/symptom listed in [Appendix 10 - COVID-19 signs/symptoms checklist](#) within the last 24 h;

4. Patient already admitted or requiring hospital care* for symptomatic COVID-19, for which at least one antiviral has failed[†] or cannot be used[‡], after a minimum washout period of 24h for small molecules (e.g., remdesivir, molnupiravir, nirmaltrevir/ritonavir) and 5 days for antiviral monoclonal antibodies (e.g., tixagevimab + cilgavimab) or convalescent plasma.

* The definition of hospital care is based on the need to use a hospital environment (hospital ward, day hospital) for treatment administration and/or clinical monitoring of the patient with COVID-19.

[†] Failure of a prior antiviral is defined as a documented lack of clinical response, plus evidence of persisting positivity for SARS-CoV-2 in an appropriate biological sample, determined by a regulatory approved test, collected no more than 3 days prior to study randomisation, with either a Ct value ≤ 30 (RT-PCR) or a positive antigen test.

[‡] Contraindication, absence of labelled indication, guidelines, or drug unavailability.

5. Adequate bone marrow, liver, kidney, and metabolic function, defined by the following tests performed at local laboratory:
 - Absolute neutrophil count $\geq 500/\text{mm}^3$ ($0.5 \times 10^9/\text{L}$);
 - Platelet count $\geq 50\,000/\text{mm}^3$ ($50 \times 10^9/\text{L}$);
 - Alanine transaminase (ALT) $\leq 3 \times$ upper limit of normal (ULN) ($\leq 5 \times$ ULN if pre-existent liver involvement by the underlying disease);
 - Serum bilirubin $\leq 1.5 \times$ ULN (or direct bilirubin $< 1.5 \times$ ULN when total bilirubin is above ULN);
 - Estimated glomerular filtration rate $\geq 30 \text{ mL/min}$ [CKD-EPI Creatinine Equation (2021)] (85).

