	ASSESSMENT/PROCEDURES	TIME
	for specific gravity, blood, pH, proteins, bilirubin, glucose, ketones, nitrites, and qualitative analysis of the sediment).	clinically indicated for AE evaluation. When applicable, these assessments should be performed before treatment administration.
Inflammatory and immunological biomarkers in blood (central laboratory)	Luminex® Multiplex cytokine assessment.	Days 1, 2, 4 (± 1).
Anti-SARS-CoV-2 (central laboratory)	IgG/M anti-protein S and N.	Day 1 previous to treatment administration.
	T-cell response (IFN- γ) to SARS-CoV-2 S-protein (Quantiferon®).	
Detection of SARS-CoV-2	qRT-PCR in oro/naso-pharyngeal exudates (central laboratory).	Day 1, 4 (± 1).
	Rapid Antigen Test (at site).	Day 1, 4 (± 1).
ECG**	Cardiac rhythm will be identified in ECG intervals of at least 30 seconds of duration, PR interval, QT interval (raw), heart rate and QRS complex, with specialist assessment/judgment of further evaluation if appropriate.	At screening or Day 1 (previous to treatment administration). Repeat on Day 4 (± 1), and whenever clinically indicated for AE evaluation.
Chest X-ray	Qualitative evaluation and Brixia score (See Appendix 9 – Brixia Score). (Submission to central review)	At screening or Day 1 (previous to treatment administration). Repeat whenever clinically indicated for AE evaluation.
ISARIC-4C deterioration score	Appendix 4	At screening or Day 1 (previous to treatment administration).
Pharmacokinetics (central laboratory)	(See details in Section 7.6).	Days 1, 3, 4 (see details in Section 7.6).
Antiviral Treatment administration	(See details in Section 6.1).	Days 1-3 in the experimental arm.⁹

	ASSESSMENT/PROCEDURES	TIME
		From Day 1 (date of randomisation) to the last dose of the antiviral therapy in the control arm. [¥]
Survival status		Throughout the treatment period.
Hospitalisation status		Throughout the treatment period.
Adverse events	As per NCI-CTCAE v.5***	Throughout the treatment period.

* Central laboratory for all the tests, except for screening.

** Triplicate.

*** The “AE form” will be used to report signs and symptoms and medical history in case of any significant change (improvement or worsening) during the study, as well as for events that occur after the first drug infusion or any event related to a study procedure within the study period (according to ICH guidelines).

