6.3.2 Prohibited Medications/Therapies

- Other investigational agents.
- Concomitant use of plitidepsin and antiviral treatments for COVID-19.

- Strong CYP3A4 inhibitors and inducers throughout plitidepsin treatment period and until 24-h washout period ([Appendix 3 - Inhibitors and Inducers of CYP3A4](#)), unless medical judgement that they are for the patient's best interest.

Investigator may decide to stop the study treatment at any time after the first dose of plitidepsin and initiate other antiviral treatments for COVID-19.

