Percentage of patients receiving immune-modulating drugs on Days 1, 4 (± 1), 8 (± 1), 15 (± 1), 30 (± 2), and 60 (± 3).	-Frequencies	-FAS population
Time to onset of additional (i.e., not present at baseline) antiviral drugs.	-Kaplan-Meier (unstratified)	-FAS population

Endpoints	Analyses	Population
Percentage of patients receiving subsequent antiviral drugs (i.e., not present at baseline) on Days 4 (± 1), 8 (± 1), 15 (± 1), 30 (± 2), and 60 (± 3).	-Frequencies	-FAS population
Percentage of patients with a new infection by Days 4 (± 1), 8 (± 1), 15 (± 1), 30 (± 2), and 60 (± 3).	-Frequencies	-FAS population
Cumulative mortality (all-cause and related to COVID-19) by Days 4 (± 1), 8 (± 1), 15 (± 1), 30 (± 2), and 60 (± 3).	-Frequencies	-FAS population
Percentage of patients in each study group who require subsequent admission within 30 days of initial end of hospital care [up to day 60(± 3)], related to either COVID-19 or COVID-19 therapy.	-Frequencies	-FAS population
Change respect to Day 1 in the viral load of SARS-CoV-2, measured by RT-PCR, by Days 4 (± 1), 8 (± 1), 15 (± 1), 30 (± 2), and 60 (± 3), in each study group.	-Summary statistics	-FAS population
Percentage of patients in each study group with undetectable viral load, by Days 4 (± 1), 8 (± 1), 15 (± 1), 30 (± 2), and 60 (± 3).	-Frequencies	-FAS population
Time to either undetectable viral load of SARS-CoV-2 or > 2 logs reduction respect to Day 1.	-Kaplan-Meier (unstratified)	-FAS population
Change respect to baseline in inflammatory biomarkers (C-reactive protein [CRP], procalcitonin, lactate dehydrogenase [LDH], ferritin, neutrophil-to-lymphocyte ratio, and multiplex cytokines assay,	-Summary statistics	-FAS population

Endpoints	Analyses	Population
by Day 4 (± 1), 8 (± 1), 15 (± 1) and 30 (± 2) and 60 (± 3).		
Change respect to baseline in individual serological assessments against SARS-CoV-2, by Days 30 (± 2), and 60 (± 3).	-Summary statistics	-FAS population
Change respect to baseline in individual T-cell response against SARS-CoV-2 by Days 30 (± 2), and 60 (± 3).	-Summary statistics	-FAS population
Change respect to baseline to Days 15 (± 1), and 30 (± 2) in chest X-ray findings (Brixia score, centrally assessed) (Protocol Appendix 9 – Brixia Score).	-Summary statistics	-FAS population
Percentage of patients requiring modification of the therapy (drugs, dose or schedule) for the underlying disease.	-Frequencies	-FAS population

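### The anti-S IgG part of the exploratory serology endpoint cannot tell infused antibody from the patient's own response, and the plan gives anti-N no role in separating them

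*Protocol*

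**What the plan says.** Protocol 2.3.3 sets an objective of comparing the arms on immune response against SARS-CoV-2. Protocol 3.3.3 serves it with "Change respect to baseline* in individual serological assessments against SARS-CoV-2" at Days 30 and 60, next to a separate T-cell endpoint. The panel in Protocol 5.7 is "IgG/M anti-protein S and N", taken on Day 1 before treatment; 5.8 and 5.9 repeat it at Days 30 and 60.

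On products that contain antibody, the protocol says the following:

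- Section 4.1 handles them with the antivirals and requires a washout of "5 days for antiviral monoclonal antibodies (e.g., tixagevimab + cilgavimab) or convalescent plasma" before entry. Section 1.1 treats monoclonals as spike-directed, speaking of "developing MAbs that target conserved regions of spike receptor-binding-domain".
- Section 3 states: "Patients randomised to the control arm may receive a regulatory-approved antiviral treatment in addition to the BSC". Antiviral treatment starts on the randomisation date.
- Section 6.3.2 prohibits "Concomitant use of plitidepsin and antiviral treatments for COVID-19", but lets the investigator stop plitidepsin and start another antiviral.
- Immunoglobulin is not on the prohibited list, so 6.3.1 leaves it to the investigator in both arms.

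SAP Table 3 (section 11.8) assigns "Change respect to baseline in individual serological assessments against SARS-CoV-2" summary statistics in the FAS. The text above that table carries the treatment-policy strategy over to the other endpoints where applicable. SAP 6.0 drops significance tests, and SAP 11.10 drops subgroup outputs.

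**The concern.** Treatment policy is a sensible choice for mortality. For anti-S IgG the later treatment can itself be the substance that the assay measures. An infused anti-spike IgG is read as though the patient had made it, and nothing in the supplied text flags, separates or excludes such values.

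This can happen in two ways. Antibody given on Day 1 is open to controls but not alongside plitidepsin, so it can raise anti-S change mainly in controls. Antibody given before entry sits in the baseline value and declines afterwards, which pulls the change downward and can hide a real response in either arm.

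What is at stake is how the table is read. SAP 6.0 still expects readers to compare the arms on the numbers. A weaker anti-S change under plitidepsin could be taken as a poorer humoral response when it reflects only who was infused with antibody.

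**Working it through.** **Plan figure.** The documents give no number for this endpoint, so there is nothing to reproduce. The check sets out who can receive what, then gives illustrative arithmetic with stated assumptions.

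**1. Exposure by product and arm**

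| Product | Effect on the panel | Control | Plitidepsin |
|---|---|---|---|
| Anti-spike IgG monoclonal | Raises anti-S IgG; not anti-N, not IgM | Allowed from Day 1 if approved and clinically indicated | Not with plitidepsin; possible after stopping |
| Convalescent plasma | Can raise anti-S and anti-N | As above, if it counts as an approved antiviral | As above |
| Immunoglobulin | Can raise anti-S and anti-N | Allowed | Allowed |

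The built-in difference between arms comes from the first row, and from the second if plasma counts as an antiviral.

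**2. Antibody remaining.** The documents give no half-life h, so I assume 21 days with a range of 7 to 90. Fraction remaining r = 0.5^(t/h). Day 1 is the randomisation date, so Day 30 is t = 29 and Day 60 is t = 59.

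| Interval | h = 7 | h = 21 | h = 90 |
|---|---|---|---|
| 5-day washout | 61% | 85% | 96% |
| Day 1 to Day 30 | 6% | 38% | 80% |
| Day 1 to Day 60 | 0.3% | 14% | 63% |

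The washout leaves most of a pre-entry dose in the baseline at every assumed half-life. Whether a Day 1 dose still matters at Day 30 depends strongly on the half-life.

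**3. Masking by pre-entry antibody.** In the limiting case of a wholly passive baseline, the patient's own antibody must reach 1 − r of the baseline value just to show zero change. At Day 30 that is 1 − 0.06 = 94%, 1 − 0.38 = 62% or 1 − 0.80 = 20% for h = 7, 21 or 90. Any smaller true response appears as a decline.

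**4. Inflation by Day 1 antibody.** Simplify to the proportion with an apparent anti-S response. Let s be the true response, equal in both arms, and m the share of controls infused. Assume no one is infused in the plitidepsin arm and every infused control reads as a responder. Controls then show s + (1 − s)m, and the spurious gap is (1 − s)m.

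| | s = 10% | s = 30% | s = 50% |
|---|---|---|---|
| m = 10% | 9 points | 7 | 5 |
| m = 20% | 18 | 14 | 10 |
| m = 50% | 45 | 35 | 25 |

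For example, 0.90 × 0.20 = 0.18. For a given m these are upper limits, because some infused antibody will have decayed and some plitidepsin patients may receive it later.

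**5. What is known about m.** Nothing. The compassionate-use series in the protocol background reports sotrovimab in 12 of 33 patients (36%) and immunoglobulin in 6 of 33 (18%). All 33 received plitidepsin, so these figures show only that such products are used in this kind of population.

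**The case against.** The strongest reply is that little depends on this.

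- **Only part of the panel is affected.** Anti-N and IgM are not raised by an anti-spike IgG monoclonal, and the T-cell endpoint is separate. This stands. A reader might infer that the whole immune-response assessment is invalid, and the documents do not support that.
- **Exposure in controls may be low.** Antivirals are given only if clinically indicated and must be approved, and Protocol 1.1 reports a marked loss of activity of many monoclonals against Omicron. This stands. A reader might infer from the compassionate-use series that 36% to 55% of trial patients are affected (55% being (12 + 6)/33 with no overlap). Those patients were all treated with plitidepsin, so the series gives no control-arm rate.
- **The direction of bias is not fixed.** Pre-entry antibody is subject to the same washout before randomisation and is not expected to differ by arm. Immunoglobulin is open to both arms, and plitidepsin patients may start antivirals after stopping. This stands. Only the Day 1 route favours controls, so it cannot be said that the table will make plitidepsin look immunosuppressive. Nor does the no-immunosuppression argument in Protocol 1.2.1.3.2 and 1.3 rest on antibody titres.
- **No decision depends on it.** The endpoint is exploratory, SAP version 3.0 is descriptive after early closure, and medications are listed, so a careful reader could trace affected patients. This limits the severity. It does not make the summary table interpretable on its own.
- **Assay-level handling may exist.** Protocol 7.1.4 refers to validated central tests, and Appendices 8 and 13 and the laboratory manual are not in the supplied text. A rule there cannot be ruled out.

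**Conclusion.** The concern holds for the anti-S IgG component. Followed as written, the plan tabulates infused anti-spike antibody as immune response. Day 1 use can inflate anti-S change mainly in controls, and pre-entry use can mask a true response in either arm.

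The washout result is the firmest: about 61% to 96% of a pre-entry dose remains after 5 days, given assumed half-lives of 7 to 90 days. The net effect on the comparison of arms is unknown, because control-arm antibody use is not given. The gaps of 5 to 45 points are illustrations, not estimates.

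Severity is minor. The marker that would separate a monoclonal from the patient's own antibody is already being measured, but the plan gives it no defined role.

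**What to change.** Amend SAP 8.3 and Table 3 as follows.

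1. Name anti-N as the main marker of endogenous antibody response, in the FAS.
2. Keep the full-FAS anti-S table.
3. Add anti-S change by arm, split by a flag for any anti-spike monoclonal, convalescent plasma or immunoglobulin between a fixed look-back before Day 1 (for example 6 months) and the sample date.
4. Apply the plasma and immunoglobulin part of the flag to anti-N as well.
5. Label the split as non-randomised, because receipt after Day 1 is a post-randomisation event.

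Simply excluding recipients would be worse. It would select patients on treatment received after randomisation, possibly more in controls, and so break the randomised comparison.

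The cost is one derived medication flag, smaller strata, and a supportive table that is not a randomised comparison. No new data and no change to patient care are needed. Protocol 5.5.1 and 5.8 and SAP 11.5 already call for prior, concomitant and subsequent medication. Protocol 6.3.1 speaks only of the on-treatment period, so completeness of follow-up medication should be checked before the flag is built.

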4. SELECTION OF PATIENTS

Patients must fulfill all the following inclusion/exclusion criteria to be eligible to participate in the study.

4.1 INCLUSION CRITERIA

To be eligible for inclusion into this study, each patient must fulfil the following inclusion criteria within 48 hours prior to randomisation:

General inclusion criteria:

1. Signed informed consent obtained prior to initiation of any study-specific procedures and study treatment;
2. Patient aged ≥ 18 years;
3. Patient diagnosed COVID-19, with the following characteristics: a) A regulatory approved test, collected no more than 3 days prior to study randomisation, with either a Ct value ≤ 30 or a positive antigen test;
b) Presence of any of the selected signs/symptom listed in [Appendix 10 - COVID-19 signs/symptoms checklist](#) within the last 24 h;

4. Patient already admitted or requiring hospital care* for symptomatic COVID-19, for which at least one antiviral has failed[†] or cannot be used[‡], after a minimum washout period of 24h for small molecules (e.g., remdesivir, molnupiravir, nirmaltrevir/ritonavir) and 5 days for antiviral monoclonal antibodies (e.g., tixagevimab + cilgavimab) or convalescent plasma.

* The definition of hospital care is based on the need to use a hospital environment (hospital ward, day hospital) for treatment administration and/or clinical monitoring of the patient with COVID-19.

[†] Failure of a prior antiviral is defined as a documented lack of clinical response, plus evidence of persisting positivity for SARS-CoV-2 in an appropriate biological sample, determined by a regulatory approved test, collected no more than 3 days prior to study randomisation, with either a Ct value ≤ 30 (RT-PCR) or a positive antigen test.

[‡] Contraindication, absence of labelled indication, guidelines, or drug unavailability.

5. Adequate bone marrow, liver, kidney, and metabolic function, defined by the following tests performed at local laboratory:
 - Absolute neutrophil count $\geq 500/\text{mm}^3$ ($0.5 \times 10^9/\text{L}$);
 - Platelet count $\geq 50\,000/\text{mm}^3$ ($50 \times 10^9/\text{L}$);
 - Alanine transaminase (ALT) $\leq 3 \times$ upper limit of normal (ULN) ($\leq 5 \times$ ULN if pre-existent liver involvement by the underlying disease);
 - Serum bilirubin $\leq 1.5 \times$ ULN (or direct bilirubin $< 1.5 \times$ ULN when total bilirubin is above ULN);
 - Estimated glomerular filtration rate $\geq 30 \text{ mL/min}$ [CKD-EPI Creatinine Equation (2021)] (85).
6. Females of childbearing potential must have a negative serum or urine pregnancy test by local laboratory at screening and must be non-lactating.
7. Females of child-bearing potential must use highly effective contraceptive methods, while on study treatment and for 6 months after last dose of plitidepsin. Fertile males with partners of childbearing potential must use effective contraception, while on study treatment and for 6 months after last dose of plitidepsin (See [Appendix 2 – Contraception and pregnancy testing](#)). Patients in the control arm must follow contraception methods indicated in the approved product information (summary of product characteristics [SmPC] or leaflet). If no information is available in the approved product information, patients in the control arm must use highly effective (females of child-bearing potential) and effective (fertile males with partners of child-bearing

potential) contraception for at least one week after the study completion or the time indicated based on the investigator's discretion.

Group-specific inclusion criteria:

- **Group 1 – Patients receiving, within the last 30 days, immune-suppressive therapy due to haematopoietic or organ transplantation.**
 - Haematopoietic transplantation.
 - Solid Organ Transplantation:
 - Lung / intestinal.
 - Other.
- **Group 2 – Patients receiving B-cell depleting therapies within the last 6 months*.**
Includes (but is not limited to):
 - Monoclonal antibodies (mAbs) targeting CD19, CD20, CD38, or CD52 (e.g., rituximab, ocrelizumab, ofatumumab, daratumumab, alemtuzumab).
 - B-cell activating factor (BAFF) inhibitors (e.g., belimumab).
 - Bruton's tyrosine kinase (BTK) inhibitors (e.g., evobrutinib, ibrutinib).
 - Chimeric antigen receptor T cell therapy (CAR-T) (e.g., anti-CD19 CAR-T cell).

*Time restriction is not applicable for CAR-T cell therapy.

- **Group 3 – Patients receiving, within the last 30 days, other immune-suppressive therapies.**
 - Other immunosuppressive therapies not including B-cell depleting agents for the treatment of auto-immune disorders.
 - Chemotherapy or targeted therapies with immunosuppressive potential for solid tumours or haematological disorders.
 - Chronic glucocorticoids (i.e., equivalent to prednisone \geq 20 mg/day for more than 1 month).
- **Group 4* – Other situations with immunodeficiency.**
 - Primary immune deficiencies.
 - Human immunodeficiency virus (HIV) infection, with CD4 $^{+}$ T lymphocyte $<$ 200 cells/ μ L in the last month.
 - Radiation therapy within the last 3 months- requires documentation of ALC $<$ 500 cells/ μ L.
 - Haematological neoplasia or myelodysplasia not currently receiving any therapy
 - Other situations with a documentation of ALC $<$ 500 cells/ μ L.

*Not applicable in Spain

Further information about groups and immunosuppressive therapies can be found in [Appendix 12 – Definition of NEREIDA Study Groups and lists of immunosuppressive treatments.](#)

